8.7.2 Statistical methods

A descriptive analysis will be conducted on all study endpoints for which data has been collected both on FAS (GAS for primary endpoint) and per subgroups of interest as long as that the sizes of the subgroups are relevant for statistical estimations.

The following statistics will be provided for quantitative variables: number of patients with non-missing and missing values, mean, standard deviation, median, first quartile (Q1), third quartile (Q3), minimum and maximum value, mode (for discrete quantitative variables with limited variability).

For qualitative variables, the number and proportion of each variable modality will be provided together with the number of missing values. Proportions will be computed based on the population with non-missing data. Missing data will not be imputed or replaced.

Exploratory comparison between study subgroups might be considered. Statistical tests will be based on the type and the variables. All comparison tests will be two-tailed with a standard type 1 error threshold of 5% (significance level).

In order to reach the exploratory objectives, logistic regressions will be implemented to identify factors linked to Norditropin[®] growth evolution (reaching height > -2 SDS) and patients' HRQoL. The clinically relevant explanatory variables will be first tested with univariate regression. The selected variables will be processed in the multivariate regression (backward selection) and the odds-ratio with their 95% confidence interval will be used for interpretation when the variable effect is significant (5% threshold for p-value).

In addition, a mixed model will be developed to explore HRQoL scores evolution over the follow-up. Patient effect will be considered as random effect.

The patients will be enrolled in the study over a variable period limited to 24 months. The probability that a patient is included in the cohort is greater when the patient has a higher number of annual visits. This study design therefore presents several biases related to:

- the heterogeneous duration of patients' inclusion which depends on the activity size of each participating site;

- the probability that a patient is included in the cohort which depends on the frequency of annual visits.

In order to take into account the biases associated with this study design and be able to extrapolate results at the national level, adjustments will be made for descriptive analyses over the cohort using weights applied at center and patient level.

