7.3 Exploratory objectives

The exploratory objectives are as follows:

- To identify driving factors that are associated with HRQoL
- To identify driving factors that are associated with change in height (SDS) over a 4 year* period

8 Research methods

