8.1 Study design

This study is a PASS. This is a non-interventional registry of children treated with Norditropin® for short stature due to NS. This study aims to provide data on long-term growth evolution and safety of Norditropin® as well as HRQoL data. This registry will include the entirety of children treated with Norditropin® for short stature due to NS over the inclusion period. In consequence, this registry will enroll both patients who received Norditropin® before its marketing authorization for short stature due to NS in France and patients who received Norditropin® after its approval.

This study presents both a prospective and retrospective design. Data will be collected for 3 groups of patients:

- Incident patients: Children initiating Norditropin® upon their inclusion in the study.
- Prevalent patients:
 - Children who were already treated with Norditropin® before their inclusion in the study and finished their growth upon their inclusion. For these patients, all data will be collected retrospectively from medical records.
 - Children who were already treated with Norditropin® before their inclusion in the study and who did not finish their growth upon their inclusion. For these patients, data will be collected both retrospectively and prospectively.

HRQoL data will be collected on incident patients only.

The inclusion period will last for 24 months and patients will be followed-up for 4 years with possibility of extension for patients who did not reach AH. This will allow to provide interim results on October 2025 to the HAS.

All information will be collected as per physicians' routine of care and as this study is non-interventional, neither clinical interventions nor laboratory assessments will be imposed as per this protocol.

* The follow-up period in this study is 4 years with possibility of extension for patients who did not reach adult height.

[figure not shown]

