8.1.1.3 Exploratory endpoints

Table 8 Exploratory endpoints

Title of endpoint	Time frame	Unit
Improvement of HRQoL (PedsQL score)	End of follow-up	Y/N
Height at end of follow-up >-2SDS	End of follow-up	Y/N

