The PedsQL is a widely used 23-items generic questionnaire that assesses the HRQoL in children and adolescents (2-18 years) from the child- and parent perspective. This questionnaire is multidimensional measuring physical (8 items), emotional (5 items), social (5 items) and school functioning (5 items). Responses are assessed using a five-point Likert scale (0 = never a problem; 1 = almost never a problem; 2 = sometimes a problem; 3 = often a problem; 4 = almost always a problem) (3). The PedsQL questionnaire is applicable for healthy school and community populations, as well as paediatric populations with acute and chronic health conditions, which proved satisfactory internal consistency reliability ($\alpha = 0.88$ child, 0.90 parent report for the total scale score) (4). The PedsQL total score is computed as the sum of all the items. Items will be transformed to 0-100 scale so that higher scores indicate better HRQoL

Evaluation of PedsQL will be performed at baseline visit and at annual follow-up visits. Baseline PedsQL score will be compared with those taken after 12, 24, 36 and 48 months of Norditropin® treatment.

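### The regression for the height objective models attained height above -2 SDS rather than change in height SDS, and the HRQoL selection model would run on about 25 children

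*Protocol*

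**What the plan says.** Protocol 7.3 sets two exploratory objectives: "To identify driving factors that are associated with change in height (SDS) over a 4 year* period" and "To identify driving factors that are associated with HRQoL".

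Table 8 (8.1.1.3) turns both into Y/N endpoints at end of follow-up. For height it is "Height at end of follow-up >-2SDS". For HRQoL it is improvement in the PedsQL score.

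Section 8.7.2 gives the method for reaching these objectives: "logistic regressions will be implemented to identify factors linked to Norditropin[®] growth evolution (reaching height > -2 SDS", and it applies the same method to HRQoL. Clinically relevant variables are screened one at a time, and those selected enter a multivariable model with backward selection at the 5% level. A mixed model with a random patient effect is added for the course of HRQoL scores. No model of change in height is named.

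On the HRQoL data, 8.1 states "HRQoL data will be collected on incident patients only". On scoring, 8.2.10 states "The PedsQL total score is computed as the sum of all the items" and then that items are put on a 0-100 scale. Table 10 (8.3) gives the score a range of 0 to 100.

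**The concern.** Attained height SDS is baseline height SDS plus the change. A child who goes from -2.1 to -1.9 counts as a success after gaining 0.2 SDS. A child who goes from -4.0 to -2.2 counts as a failure after gaining 1.8 SDS. A variable that only marks which children started taller will therefore look like a driver of growth, although the objective asks about change. Section 8.2.4 sets no height criterion, so a child already above -2 SDS at start can also count as a success.

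For HRQoL, the outcome exists only in incident children. The protocol's own recruitment figures leave few of them, and stepwise selection on so few children gives unstable, exaggerated odds ratios.

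At stake are the answers to both exploratory objectives. The registry could report factors for growth that are only correlates of starting height, and factors for HRQoL that are mostly selection noise.

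**Working it through.** **The protocol's own numbers (8.5).** Included: (50 + 30 × 10) × 30/38 × 0.80 = 221. Evaluable for height: 221 × 0.80 = 177. Both reproduce. The 221 is reached only if the 50 incident children are discounted too; leaving them whole gives 50 + 300 × 30/38 × 0.80 = 239. The planning SD of change is 0.20 × 1.14 = 0.228 SDS.

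**Height: inputs.** From 8.5: n = 177 and mean gain 1.14. Assumed: baseline height SDS drawn from N(-3, 0.6) and cut at -2, because the protocol gives no baseline distribution. The cut leaves a variance of about 0.294. SD of change: 0.228 from the protocol, plus 0.6 and 0.9 as assumptions to show the range. Success is baseline + change > -2.

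**Height: share of baseline in final height.** With change independent of baseline, share = 0.294 / (0.294 + SD²):
- SD 0.228: 0.294 / (0.294 + 0.052) = 85%
- SD 0.6: 0.294 / (0.294 + 0.36) = 45%
- SD 0.9: 0.294 / (0.294 + 0.81) = 27%

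**Height: the univariate screen.** Take a factor correlated 0.5 with baseline height and with no effect on change. It is significant at 5% in the univariate logistic model in about 100%, 98% and 81% of simulated studies at those three SDs. The protocol gives no p-value for the screen; a threshold looser than 5% would flag more.

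**Height: power for a true binary factor worth 0.3 SDS, present in half the children** (simulated, accurate to a few points):

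| SD of change | Linear on change, with baseline | Logistic, with baseline | Logistic, without baseline |
|---|---|---|---|
| 0.228 | 100% | 99% | 74% |
| 0.6 | 92% | 60% | 48% |

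**HRQoL: number of children.** 50 × 30/38 × 0.80 = 31.6 incident children included; × 0.80 = 25.3 with an outcome at end of follow-up. The last 0.80 is the protocol's evaluability rate for height, borrowed here because none is given for PedsQL. Alternatives:
- 24 with the 168/224 = 75% completion from 8.2.3
- 32 with no loss
- 40 if all 50 are included and 80% retained
- 50 with no discount or loss

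**HRQoL: what that supports.** With 25 children the smaller outcome class holds about 12 if half improve (25 × 0.5 = 12.5), and 7 to 8 if 30% or 70% do (25 × 0.3 = 7.5). By the usual rule of ten events per variable, that is about one variable. With 50 children it is 15/10 to 25/10, or 1.5 to 2.5. In a simulation of the planned procedure with 25 children and ten null candidates (an assumed number), at least one false factor was retained in 21% to 33% of runs, depending on the screening threshold. A true odds ratio of 2 per SD (log 0.69) was selected in about 23% of runs, and its median log odds ratio when selected was about 1.5.

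**PedsQL score.** Summing 23 items each on 0-100 gives 0 to 23 × 100 = 2300, which is not the range in Table 10. A sum also falls with each unanswered item, and 8.7.2 rules out imputation.

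**The case against.** The strongest reply is that these are exploratory models in a descriptive registry, and that 8.7.2.3 leaves their detail to the SAP. Height at start is collected (Table 9) and may well be a candidate. If it is retained, backward selection would usually remove a factor that acts only through baseline. The -2 SDS threshold has clinical meaning: section 6.1 uses it for the reimbursed population. Change in height SDS is also described as the primary endpoint, overall and by treatment duration (8.7.2.1).

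Much of this stands. The covariate list and the cut-off for "Improvement of HRQoL (PedsQL score" may properly sit in the SAP, so their absence is not claimed as a defect. But the protocol already fixes the outcome, the model family and the selection method, and those are what miss the objective. Adjusting for baseline would reduce the false flags, but the odds ratio would still describe crossing a line rather than the size of the change. Section 8.9.3 speaks of regression and mixed models for HRQoL and long-term height together, yet 8.7.2 ties the mixed model to HRQoL scores only.

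A reader might also infer that HRQoL is analysed only as Y/N. It is not: a mixed model on scores is planned, and change in PedsQL score is a secondary endpoint (Table 7). However, 8.7.2 gives that model no covariates and describes its purpose as following the scores over time.

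The PedsQL wording is loose rather than a sign that 0-2300 would be reported. It still contradicts Table 10.

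**Conclusion.** The point holds for both objectives. For height, the only regression outcome fixed in the protocol is attained height above -2 SDS, while the objective is change. The planned screen would flag a pure correlate of baseline height in about 81% to 100% of studies over the SDs examined. This assumes baseline N(-3, 0.6) cut at -2, a correlation of 0.5 and 177 evaluable children.

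A reader might go further and conclude that the height model mainly reflects baseline height. The documents support that only at the protocol's small planning SD. Baseline's share of the variance is 85% there, 45% at SD 0.6 and 27% at SD 0.9. The loss of power likewise depends on the SD: at 0.228 a baseline-adjusted logistic model loses almost nothing (99% against 100%), while at 0.6 it falls to about 60% against 92%.

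For HRQoL, univariate screening and backward selection on about 25 children (24 to 50) supports one or two variables at most. The sum definition of the PedsQL total cannot be reconciled with the 0-100 range.

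Because the analyses are exploratory, this should be corrected but does not threaten the primary result.

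**What to change.** - **Height (8.7.2, Table 8).** Make linear regression of change in height SDS, adjusted for baseline height SDS, age at start and sex, the model for the height objective. Report height above -2 SDS as a described proportion among children below -2 SDS at start.
- **HRQoL (8.7.2).** Drop the logistic model with backward selection. Put the baseline score and two or three pre-chosen covariates into the mixed model already planned.
- **PedsQL (8.2.10).** Define the total as the mean of the answered items on the 0-100 scale, in line with Table 10.

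The cost is wording in the protocol and the SAP. Baseline height, age, sex and annual PedsQL scores are already collected. The downside is that an odds ratio for the clinical -2 SDS threshold is no longer the main exploratory result, although the proportion reaching it is still reported.

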8.5 Study sample size

This study will set up a registry that aims to include all eligible patients treated by Norditropin® for short stature due to Noonan syndrome.

No sample size calculation is required as this registry aims to include all patients fulfilling the sets of selection criteria defined.

According to experts' input, a maximum of 50 eligible incident patients could be included during the 24 months inclusion period. It is expected that the number of eligible patients initiating Norditropin® before 2020 would be lower since that there was no market authorisation for this indication yet and would not exceed 30 patients per year. Considering that eligible prevalent patients initiated Norditropin® from 2010, that 79% of solicited sites will be participating in the study (30 sites over 38) and that 80% of eligible patients will be included (excluding opposition, patient not regularly followed by this site), it is estimated that a maximum of 221 patients will be included in the registry.

Finally, the proportion of evaluable patients for the primary criteria (patients that have height measurements until the end of their 4 years follow-up or adult height) is planned to be 80%. Therefore, it is estimated that this study will enrol a maximum of 177 patients evaluable for the primary criteria.

The height variation (in SDS) after 4 years of treatment has been evaluated in the ANSWER® Program (observational study) at 1,14 (0,13) SDS. The change in height SDS is estimated with a 11,4% coefficient of variation (ratio of standard deviation over mean).

The following table presents the precision in primary criteria measurement (with a 2-sided 95% confidence interval (CI)) for the estimation of mean height variation in SDS considering a 20% coefficient of variation. The primary criteria will be estimated with a 2.95% precision. This high level of precision enables to perform subgroup analysis with also a satisfying precision.

Table 11 Precision of the primary criteria depending on the number of evaluable patients

Sample size	150	160	170	177	190	200
Precision for 95% CI	3.2%	3.1%	3.0%	2.95%	2.85%	2.78%

The sample size (n) is calculated based on the normal approximation using the following formula:

$$N = z_{1-\alpha/2}^2 \frac{cv^2}{\epsilon^2}$$

where:

- z is the standard normal distribution's quantile (for $\alpha=5\%$),
- CV is the coefficient of variation (20%),

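### The 2.95% planning precision in Section 8.5 is for an unweighted, independent sample, whereas Section 8.7.2 plans centre- and patient-level weights over about 30 sites

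*Protocol*

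**What the plan says.** Section 8.5 of the protocol tabulates the precision of the primary estimate (Table 11) "for the estimation of mean height variation in SDS considering a 20% coefficient of variation". Precision there means the half-width of the two-sided 95% confidence interval as a share of the mean. The method is stated: "The sample size (n) is calculated based on the normal approximation using the following formula", namely N = z²·CV²/ε². On numbers, "it is estimated that this study will enrol a maximum of 177 patients evaluable for the primary criteria", and Table 11 gives 2.95% at that size. Section 8.5 then draws a conclusion from it: "This high level of precision enables to perform subgroup analysis with also a satisfying precision".

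Section 8.7.2 makes every endpoint a descriptive analysis, the primary one on the Growth Analysis Set. It names two sources of bias in the way patients enter the cohort. One is "the heterogeneous duration of patients' inclusion which depends on the activity size of each participating site". The other is that patients seen more often each year are more likely to be included. To deal with both and to extrapolate nationally, "adjustments will be made for descriptive analyses over the cohort using weights applied at center and patient level".

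**The concern.** The two sections describe different estimators. Section 8.5 gives the precision of a plain mean of 177 independent, equally weighted patients. Section 8.7.2 plans a weighted mean of patients grouped in sites. Unequal weights raise the variance of a mean when they are unrelated to the outcome. Patients of one site who share treatment practice are also less informative than the same number of unrelated patients. Section 8.5 has no term for either effect.

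What is at stake is the planning statement itself and the use made of it. The protocol announces 2.95% as the precision to be achieved and relies on it to say that subgroups will be estimated well enough. Section 8.7.1 names treatment duration and mutated gene as the subgroups of interest. The protocol also goes to the French health authority (Section 9.2), which will read the figure as the precision of the national estimate.

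**Working it through.** **Inputs from the protocol (Section 8.5).** z = 1.96; CV = 20%; n = 177; 30 of 38 sites participating; 80% of eligible patients included. Both 20% and 177 are taken as given here.

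**Step 1: reproduce the stated figure.** Solving the protocol's formula for ε:

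ε = z·CV/√n = 1.96 × 0.20/√177 = 2.946%, stated as 2.95%.

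The other columns of Table 11 also reproduce within rounding: 3.20, 3.10, 3.01, 2.84 and 2.77%, against 3.2, 3.1, 3.0, 2.85 and 2.78%. The table therefore corresponds to a design effect of exactly 1.

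**Step 2: add a design effect.** The usual approximation is

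deff = (1 + CV_w²) × (1 + (m − 1)·ICC), and half-width = 2.946% × √deff,

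where CV_w is the coefficient of variation of the weights, ICC the intra-site correlation, and m = 177/30 = 5.9 patients per site. The first factor treats the weights as unrelated to the outcome, and the second treats sites as equal in size. The protocol gives neither CV_w nor ICC, so **the values below are assumptions**.

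| Assumed CV_w | Assumed ICC | deff | Effective n | Half-width | On a mean of 1.14 SDS |
|---|---|---|---|---|---|
| 0 | 0 | 1.00 | 177 | 2.95% | ±0.034 |
| 0.3 | 0.01 | 1.09 × 1.049 = 1.14 | 155 | 3.15% | ±0.036 |
| 0.5 | 0.05 | 1.25 × 1.245 = 1.56 | 114 | 3.68% | ±0.042 |
| 0.7 | 0.10 | 1.49 × 1.49 = 2.22 | 80 | 4.39% | ±0.050 |

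A round design effect of 1.5 gives 2.946% × √1.5 = 3.61%, or ±0.041 SDS. Weighting alone (CV_w = 0.5, ICC = 0) gives deff 1.25 and 3.29%.

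**Step 3: the finite-population correction.** Section 8.5 implies about 50 + 10 × 30 = 350 eligible patients, since 350 × 0.79 × 0.80 = 221 and 221 × 0.80 = 177. If inference is limited to those patients, the half-width is multiplied by about √(1 − 177/350) = 0.70. This would offset a design effect of 1/(1 − 177/350) = 2.02. As a rough approximation, 3.61% becomes 3.61% × 0.703 = 2.54%, and 4.39% becomes 3.09%.

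**Step 4: the margin in the CV.** Section 8.5 cites an observed CV of 11.4% but plans with 20%. The variance ratio is (20/11.4)² = 3.08. If 11.4% were the true value, 2.95% would still be met at any design effect up to about 3.1.

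**The case against.** The strongest objection concerns what the figure is for. A reader might infer that the registry will publish a confidence interval that is too narrow and covers less than 95%. The protocol does not support that. For quantitative variables, Section 8.7.2 lists counts, mean, standard deviation, median, quartiles, range and mode. The only confidence interval it names for the analysis is the one for odds ratios. Nothing says that the Section 8.5 formula will be put around the weighted mean, and the choice of variance estimator is ordinary content for the statistical analysis plan. This part of the objection stands, so no loss of coverage can be claimed.

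Nor is it established that 2.95% is too small on balance. The registry is close to a census of its target. On the reading in Step 3, a finite-population correction could cancel a design effect of about 2. The 20% CV could also hold a reserve. Both are possible, but the protocol mentions no finite-population correction, gives no reason for moving from 11.4% to 20%, and does not present 20% as an allowance for weighting. Neither makes the stated figure the precision of the planned estimator.

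The weights may also be milder than assumed. Visits are expected every six months, inclusion is to be consecutive and exhaustive, and the window is 24 months, so inclusion probabilities could be fairly even. This affects the size of the gap and not its existence.

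Finally, Section 8.5 says that no sample-size calculation is required, so enrolment does not depend on the figure. Section 8.7.2 also limits subgroup analyses to subgroups of adequate size. Both are true and keep the consequence small, but the sentence on subgroup precision still rests on the unadjusted figure.

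**Conclusion.** The mismatch is established. The 2.95% in Section 8.5 is exactly the unweighted, independent-sample value, and Section 8.7.2 plans a weighted estimate over about 30 sites. With 20% CV and 177 patients as given, and without a finite-population correction, assumed design effects of about 1.14 to 2.2 give half-widths of about 3.15% to 4.4%. That range rests wholly on assumed values of the weight spread and the intra-site correlation.

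The practical effect is modest. At a design effect of 1.5 the half-width grows by about 0.041 − 0.034 = 0.007 SDS, and at 2.2 by about 0.016 SDS, on a mean of 1.14. The point is that a stated precision, and the subgroup claim built on it, belong to a different estimator from the one planned. It does not show that the final results will be misreported.

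**What to change.** In Section 8.5, do one of two things:

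- label 2.95% and the whole of Table 11 as values for an unweighted, independent sample; or
- restate them with an explicit assumed design effect (for example 1.5, giving about 3.6% at 177 patients), together with a finite-population correction if inference is meant only for the currently eligible patients. If the 20% CV is intended to cover the design effect, say so.

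Qualify the sentence on subgroup precision so that it depends on the size of each subgroup and on the weighting.

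If a confidence interval is reported for the weighted primary mean, base it on a variance that reflects the weights and the clustering by site. The details can sit in the statistical analysis plan.

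The cost is a few lines of wording and a standard survey procedure, with no extra patients or data. The only downside is that the stated precision becomes slightly less favourable if a design effect is declared.
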